15.8.1. Adverse Event and Laboratory Value Severity Grade Tables

| HEMATOLOGY | GRADE 1 | GRADE 2 | GRADE 3 | GRADE 4 |
|--------------------------------------|------------------------------------|------------------------------------|------------------------------------|-------------------------------------|
| | MILD | MODERATE | SEVERE | POTENTIALLY LIFE-THREATENING |
| Hemoglobin | > 9.5 - 11.0 g/dL | > 8.0 – 9.5 g/dL | 6.5 - 8.0 g/dL | < 6.5 g/dL |
| Leukocytes | 3000-3999/mm ³ | 2000-2999/mm ³ | 1000-1999/mm ³ | < 1000/mm ³ |
| Absolute Neutrophil Count | 1500-1999/mm ³ | 1000-1499/mm ³ | 500-999/mm ³ | < 500/mm ³ |
| Platelets | 75,000 - 99,999/mm ³ | 50,000 – 74,999/mm ³ | 25,000 - 49,999/mm ³ | < 25,000/mm ³ |
| Prothrombin Time (PT) | > 1.0-1.25 x ULN* | > 1.25-1.5 x ULN | > 1.5-3.0 x ULN | > 3.0 x ULN |
| Partial Thromboplastin Time (PTT) | > 1.0-1.66 x ULN | > 1.66-2.33 x ULN | > 2.33-3.0 x ULN | > 3.0 x ULN |
| Methemoglobin | 5.0-10.0 % | 10.1-15.0 % | 15.1-20.0 % | > 20% |
| | | | | (continued) |

*ULN = Upper Limit of Normal.

Modified from DMID Adult Toxicity Tables, 2001

Adverse Event and Laboratory Value Severity Grade Tables (continued)

| | GRADE 1 MILD | GRADE 2 MODERATE | GRADE 3 SEVERE | GRADE 4 POTENTIALLY LIFE- THREATENING |
|------------------------|---|---|--|---|
| CARDIOVASCULAR | | | | |
| Cardiac Arrhythmia | - | Asymptomatic/transient; dysrhythmia; no treatment req | Recurrent/persistent dysrhythmia. Symptomatic; treatment req | Unstable dysrhythmia hospitalization and treatment required |
| Hypotension | Transient orthostatic hypotension, no treatment | Symptoms correctable with oral fluid treatment | IV fluid req, no hospitalization req | Hospitalization req |
| Hypertension | Transient, increase > 20 mm/Hg; no treatment | Recurrent; chronic increase > 20 mm/Hg, treatment req | Acute treatment req; out patient hospitalization possible | Hospitalization req |
| Pericarditis | Minimal effusion | Mild/moderate asymptomatic effusion, no treatment | Symptomatic effusion, pain, ECG changes | Tamponade OR pericardiocentesis OR surgery req |
| Hemorrhage, Blood Loss | - | Mildly symptomatic; no treatment required | Gross blood loss OR 1-2 units transfused | Massive blood loss OR > 2 units transfused |

(continued)

1. Modified from (DMID) Adult Toxicity Tables, 2001

Adverse Event and Laboratory Value Severity Grade Tables (continued)

| CHEMISTRIES | GRADE 1 MILD | GRADE 2 MODERATE | GRADE 3 SEVERE | GRADE 4 POTENTIALLY LIFE- THREATENING |
|--|-------------------------|-----------------------------|---------------------------|--|
| Sodium | | | | |
| Hyponatremia | 130-135 meq/L | 123-129 meq/L | 116-122 meq/L | < 116 meq/L |
| Hypernatremia | 146-150 meq/L | 151-157 meq/L | 158-165 meq/L | > 165 meq/L |
| Potassium | | | | |
| Hypokalemia | 3.0-3.4 meq/L | 2.5-2.9 meq/L | 2.0-2.4 meq/L | < 2.0 meq/L |
| Hyperkalemia | 5.6-6.0 meq/L | 6.1-6.5 meq/L | 6.6-7.0 meq/L | > 7.0 meq/L |
| Phosphate | | | | |
| Hypophosphatemia | 2.0-2.4 mg/dL | 1.5-1.9 mg/dL | 1.0-1.4 mg/dL | < 1.0 mg/dL |
| Calcium- (Corrected For Albumin) | | | | |
| Hypocalcemia | 7.8-8.4 mg/dL | 7.0-7.7 mg/dL | 6.1-6.9 mg/dL | < 6.1 mg/dL |
| Hypercalcemia | 10.6-11.5 mg/dL | 11.6-12.5 mg/dL | 12.6-13.5 mg/dL | >13.5 mg/dL |
| Magnesium | | | | |
| Hypomagnesemia | 1.2-1.4 meq/L | 0.9-1.1 meq/L | 0.6-0.8 meq/L | < 0.6 meq/L |
| Albumin | | | | |
| Hypoalbuminemia | 3.00-3.49 g/dL | 2.50-2.99 g/dL | 2.00-2.49 g/dL | < 2.00 g/dL |
| Bilirubin (Total) | | | | |
| Hyperbilirubinemia (Total) | > 1.0-1.5 x ULN | > 1.5-2.5 x ULN | > 2.5-5 x ULN | > 5 x ULN |
| Glucose | | | | |
| Hypoglycemia | 55-64 mg/dL | 40-54 mg/dL | 30-39 mg/dL | < 30 mg/dL |
| Hyperglycemia (nonfasting & no prior diabetes) | 116-160 mg/dL | 161-250 mg/dL | 251-500 mg/dL | > 500 mg/dL |
| Triglycerides | 151-399 mg/dL | 400-750 mg/dL | 751-1200 mg/dL | > 1200 mg/dL |
| Creatinine | > 1.0-1.5 x ULN | > 1.5-3.0 x ULN | > 3.0-6.0 x ULN | > 6.0 x ULN |
| Uric Acid | | | | |
| Hyperuricemia | 7.5-10.0 mg/dL | 10.1-12.0 mg/dL | 12.1-15.0 mg/dL | > 15.0 mg/dL |
| Liver Transferases (AST, ALT, and GGT) | 1.25-2.5 x ULN | > 2.5-5.0 x ULN | > 5.0-10.0 x ULN | > 10.0 x ULN |
| Alkaline Phosphatase | 1.25-2.5 x ULN | > 2.5-5.0 x ULN | > 5.0-10.0 x ULN | > 10.0 x ULN |
| Pancreatic Enzymes | | | | |
| Amylase | > 1.0-1.5 x ULN | > 1.5-2.0 x ULN | > 2.0-5.0 x ULN | > 5.0 x ULN |
| Pancreatic amylase | > 1.0-1.5 x ULN | > 1.5-2.0 x ULN | > 2.0-5.0 x ULN | > 5.0 x ULN |
| Lipase | > 1.0-1.5 x ULN | > 1.5-2.0 x ULN | > 2.0-5.0 x ULN | > 5.0 x ULN |
| Hypoglobulinemia (IgG)* | 550-700 mg/dL | 400-549 mg/dL | 250-399 mg/dL | < 250 mg/dL |
| | | | | (continued) |

Modified from (DMID) Adult Toxicity Tables, 2001

Adverse Event and Laboratory Value Severity Grade Tables (continued)

| | GRADE 1 MILD | GRADE 2 MODERATE | GRADE 3 SEVERE | GRADE 4 POTENTIALLY LIFE- THREATENING |
|------------------------------|--|---|--|--|
| GASTROINTESTINAL | | | | |
| Nausea | Mild OR transient; reasonable intake maintained | Mod discomfort OR intake decreased for < 3 days | Severe discomfort OR minimal intake for ≥ 3 days | Hospitalization required |
| Vomiting | Mild OR transient; 2-3 episodes/day OR mild vomiting lasting < 1 week | Mod OR persistent; 4-5 episodes per day; OR vomiting lasting ≥ 1 week | Severe vomiting of all foods/fluids in 24 hours OR orthostatic hypotension OR IV treatment req | Hypotensive shock OR hospitalization required for IV treatment req |
| Diarrhea | Mild or transient; 3-4 loose stools per day OR mild diarrhea lasting < 1 week | Mod OR persistent; 5-7 loose stools per day or diarrhea lasting ≥ 1 week | Bloody diarrhea; OR orthostatic hypotension OR > 7 loose stools/day OR IV treatment req | Hypotensive shock OR hospitalization req |
| Oral Discomfort/Dysphagia | Mild discomfort, no difficulty swallowing | Difficulty swallowing but able to eat and drink | Unable to swallow solids | Unable to drink fluids; IV fluids req |
| Constipation | Mild | Moderate | Severe | Distention with vomiting |

Modified from (DMID) [Adult Toxicity Tables](#), 2001

Adverse Event and Laboratory Value Severity Grade Tables (continued)

| RESPIRATORY | GRADE 1 MILD | GRADE 2 MODERATE | GRADE 3 SEVERE | GRADE 4 POTENTIALLY LIFE- THREATENING |
|-----------------------------------|---|---|--|--|
| Cough (for aerosol studies) | Transient; no treatment | Treatment associated cough; inhaled bronchodilator | Uncontrolled cough; systemic treatment req | |
| Bronchospasm Acute | Transient; no treatment; FEV1 70% to < 80% (or peak flow) | treatment req; normalizes with bronchodilator; FEV1 50% to < 70% (or peak flow) | No Normalization with bronchodilator; FEV 25% to < 50% (or peak flow), retractions | Cyanosis; FEV1 < 25% (or peak flow) OR intubated |
| Dyspnea | Dyspnea on exertion | Dyspnea with normal activity | Dyspnea at rest | Dyspnea requiring O2 therapy |

| URINALYSIS | GRADE 1 MILD | GRADE 2 MODERATE | GRADE 3 SEVERE | GRADE 4 POTENTIALLY LIFE- THREATENING |
|---|--|---------------------------------|----------------------------------|--|
| Proteinuria | | | | |
| Dispstick Protein | 1 + | 2-3 + | 4 + | Nephrotic syndrome |
| Spot Urine: Protein:Creatinine Ratio mg/mg | 0.2-1.0 | > 1.0-2.0 | > 2.0-3.5 | > 3.5 |
| 24 Hour Urine: Protein | 200 mg - 1g loss/day | > 1-2 g loss/day | > 2-3.5 g loss/day | Nephrotic syndrome OR > 3.5 g loss/day |
| Hematuria | Microscopic only > 3 to < 10 RBC/hpf | Gross, No clots ≥ 10 RBC/hpf | Gross plus clots OR RBC casts | Obstructive OR transfusion required |

RBC = red blood cell; hpf = high power field.

Modified from [\(DMID\) Adult Toxicity Tables](#), 2001

Adverse Event and Laboratory Value Severity Grade Tables (continued)

| MISCELLANEOUS | GRADE 1 MILD | GRADE 2 MODERATE | GRADE 3 SEVERE | GRADE 4 POTENTIALLY LIFE- THREATENING |
|--|---|---|---|--|
| Fever (oral > 12 hours) | 37.7-38.5°C or 100.0-101.5°F | 38.6-39.5°C OR 101.6-102.9°F | 39.6-40.5°C OR 103-105°F | > 40.5°C OR > 105°F |
| Headache | Mild; No treatment req | Mod; or non-narcotic analgesia treatment | Severe; OR responds to initial narcotic treatment | Intractable; OR requiring repeated narcotic treatment |
| Allergic Reaction | Pruritus without rash | Localized urticaria | Generalized urticaria angioedema | Anaphylaxis |
| Cutaneous/Rash/Dermatitis | Erythema, pruritus rash OR dry desquamation | Diffuse maculopapular OR dry desquamation | Vesiculation OR moist desquamation ulceration | ANY ONE: mucous membrane involvement, suspected Stevens-Johnson (TEN), erythema multiforme, necrosis req surgery, exfoliative dermatitis |
| Local Reaction (secondary to parenteral treatment- not vaccination or skin test) | Erythema | Induration < 10 mm OR inflammation OR phlebitis | Induration > 10 mm OR ulceration | Necrosis of skin |
| Fatigue | Normal activity Reduced < 25% | Normal activity Reduced 25-50% | Normal activity reduced > 50%; cannot work | Unable to care for self |

Modified from (DMID) Adult Toxicity Tables, 2001

Adverse Event and Laboratory Value Severity Grade Tables (continued)

| NEUROLOGIC | GRADE 1 MILD | GRADE 2 MODERATE | GRADE 3 SEVERE | GRADE 4 POTENTIALLY LIFE- THREATENING |
|--------------------------------------|---|--|---|---|
| Neuro-cerebellar | Slight incoordination OR dysdiadochokinesia | Intention tremor OR dysmetria OR slurred speech OR nystagmus | Ataxia requiring assistance to walk or arm incoordination interfering with ADLs | Unable to stand |
| Neuro-psych/mood | | None | Severe mood changes requires medical intervention | Acute psychosis requiring Hospitalization |
| Paresthesia (burning, tingling, etc) | Mild discomfort; no treatment needed | Mod discomfort non-narcotic analgesia req | Severe discomfort; OR narcotic analgesia req with symptomatic improvement | Incapacitating; OR not responsive to narcotic analgesia |

| | | | | |
|---------------|---|---|--|--|
| Neuro-motor | Mild weakness in muscle of feet but able to walk and/or mild increase or decrease in reflexes | Mod weakness in feet (unable to walk on heels and/or toes), mild weakness in hands, still able to do most hand tasks and/or loss of previously present reflex or development of hyperreflexia and/or unable to do deep knee bends due to weakness | Marked distal weakness (unable to dorsiflex toes or foot drop), and mod proximal weakness ie, in hands interfering with ADLs and/or requiring assistance to walk and/or unable to rise from chair unassisted | Confined to bed or wheelchair because of muscle weakness |
| Neuro-sensory | Mild impairment sensations, (ie, vibratory, pinprick, hot/cold in great toes) in focal area or symmetrical distribution | Mod impairment mod de-sensation, (ie, of vibratory, pinprick, hot/cold to ankles) and/or joint position or mild impairment that is not symmetrical. | Severe impairment (dec or loss of sensation to knees or wrists) or loss of sensation of at least mod degree in multiple different body areas (ie, upper and lower extremities) | Sensory loss involves limbs and trunk |

| | GRADE 1 MILD | GRADE 2 MODERATE | GRADE 3 SEVERE | GRADE 4 POTENTIALLY LIFE- THREATENING |
|--------------------|-----------------|---------------------|-------------------|---|
| Lymphopenia | >0.8 (GI/L) | <=0.8 - >.5(GI/L) | <=0.5->0.2(GI/L) | <=0.2(GI/L) |
| Source: CTCAE 4.03 | | | | |

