8.3. Clinical Laboratory Analyses

Laboratory evaluations including the analyses of Chemistry laboratory tests, Hematology laboratory tests, Urinalysis, and liver function tests will be based on GSK Core Data Standards.

For laboratory analyses analytes will be analyzed and summaries and analyses will be performed based on the observed data. No imputation will be done for missing data. Baseline is defined as described in Section 5.3. See Protocol Appendix 9 for a list of laboratory parameters. Laboratory toxicity grades will be assigned based on DMID (see Section 15.8 Appendix 8: Laboratory Parameters and Toxicity Grades) by the laboratory,

with the exception of Lymphopenia (as there is no DMID grade). Lymphopenia will be graded as per CTCAE v4.03.

Calcium, will be presented as hypercalcaemia and hypocalcaemia separately (with each subject appearing in both categories) and similarly for sodium (hypernatremia, hyponatremia), potassium (hyperkalemia, hypokalemia), and glucose (hyperglycemia, hypoglycemia).

Listings will be generated for all laboratory results and for Grade 3 or Grade 4 laboratory toxicity results [L13.13 – L13.24, L23.14 - L23.26].

If a numeric laboratory value, has a non-detectable level reported in the database, then typically the numeric value is missing, and a character value starting with '<x' or '>x' is present. A numeric value will be derived using the number of decimal places in the observed character values i.e.

- 2 Decimal Places = '< x ' becomes $x - 0.01$
- 1 Decimal Place = '> x' becomes $x + 0.1$
- 0 Decimal Places = '< x' becomes $x - 1$

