8.3.2. Laboratory Toxicity \geq 2 Grade Shift Post-Baseline

Toxicity grade shifts from baseline of \geq 2 grades will be summarized during treatment for each laboratory parameter within each laboratory category (hematology, liver function, electrolytes, other chemistries, urinalysis and immunoglobulins) for Year 1 and Year 1&2 separately. The table will display the number and percentage of subjects with at least one \geq 2 grade shift as well as the specific shift categories: Grade 0 to 2, Grade 0 to 3, Grade 0 to 4, Grade 1 to 3, Grade 1 to 4 and Grade 2 to 4 [T13.57, T13.61, T13.65, T13.69, T13.72, T13.76, T23.51, T23.55, T23.59, T23.63, T23.66, T23.70].

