8.3.5. Worst Laboratory Toxicity Grade Post-Baseline

Laboratory toxicity will be graded using grades corresponding to mild, moderate, severe, and life-threatening when possible. The worst laboratory toxicity grade for each laboratory parameter within each laboratory category (hematology, liver function, electrolytes, other chemistries, urinalysis and immunoglobulins) during Year 1 and Year 1&2 separately will be presented. Data for both scheduled and unscheduled visits will be included. For calcium, sodium, potassium and glucose, grades associated with hypo- and hyper- conditions will be included [T13.56, T13.60, T13.64, T13.68, T13.71, T13.75, T23.50, T23.54, T23.58, T23.62, T23.65, T23.69].

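### Lymphopenia Grade 1 is printed without an upper limit, so if the row is applied literally, normal counts grade as lymphopenia and falls from normal to Grade 2 drop out of the two-grade worsening table

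*SAP*

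**What the plan says.** SAP Section 15.8.1 ends with a separate lymphopenia row. Its cells for Grade 1 and Grade 2, divided by the bar, read ">0.8 (GI/L) | <=0.8 - >.5(GI/L". Grade 3 then runs from above 0.2 up to 0.5 GI/L, and Grade 4 is 0.2 GI/L or less. The row is annotated "Source: CTCAE 4.03".

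SAP Section 8.3 explains why the row stands apart. Laboratory toxicity grades are DMID grades assigned by the laboratory, "with the exception of Lymphopenia (as there is no DMID grade"; the next sentence adds that "Lymphopenia will be graded as per CTCAE v4.03". Nothing further is said about who assigns this grade or from which text.

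Two planned displays use the grade. Section 8.3.5 tabulates worst post-baseline grades: "The worst laboratory toxicity grade for each laboratory parameter within each laboratory category", hematology among them. Section 8.3.2 counts worsening of at least two grades and lists six kinds of change, namely "Grade 0 to 2, Grade 0 to 3, Grade 0 to 4, Grade 1 to 3, Grade 1 to 4 and Grade 2 to 4". The RAP addendum for the end-of-study analyses keeps both hematology tables for Year 1&2, as new 23.39 (worst grade) and 23.40 (two-grade worsening).

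**The concern.** A grading scale for low counts needs a region that is not low. The other blood-count rows in Section 15.8.1 have one, because their Grade 1 stops on the normal side. The lymphopenia row does not, so a healthy count falls in the cell for mild lymphopenia.

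Two things are at stake. In the worst-grade table, true Grade 1 lymphopenia could not be told apart from a normal count in any arm. In the worsening table, a participant who starts normal and falls to Grade 2 would register a one-grade change and be left out. Arm B adds an antibody that depletes circulating B cells, and the Protocol lists prolonged B-cell suppression with infection among its risks (Section 3.3.1). A moderate fall in lymphocytes is therefore something the safety tables should be able to show by arm.

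**Working it through.** There is no power, alpha or sample-size figure to reproduce. The check applies the printed rule to counts and compares it with a bounded version.

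**Inputs**
- Printed cut-offs in GI/L, from SAP Section 15.8.1.
- Shift rule, from SAP Section 8.3.2: a change counts when post-baseline grade minus baseline grade is at least 2.
- Grade 1 in the comparison rows, from SAP Section 15.8.1: hemoglobin above 9.5 to 11.0 g/dL; leukocytes 3000 to 3999, neutrophils 1500 to 1999 and platelets 75,000 to 99,999 per mm³.
- Lower limit of normal (LLN) for lymphocytes: not in the documents. Assumed for this check only, at 0.9, 1.0, 1.2 and 1.5 GI/L.

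**Step 1: the printed rule.** For a count x, g(x) = 4 if x ≤ 0.2; 3 if 0.2 < x ≤ 0.5; 2 if 0.5 < x ≤ 0.8; 1 if x > 0.8. These intervals cover every possible count, so g(x) is never 0. By contrast, a leukocyte count of 4000/mm³ lies outside all four of its grades.

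**Step 2: the bounded rule.** h(x) = 0 if x ≥ LLN; otherwise h(x) = g(x).

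| Count (GI/L) | Printed g | Bounded h, LLN 0.9 / 1.0 / 1.2 / 1.5 |
|---|---|---|
| 0.1 | 4 | 4 / 4 / 4 / 4 |
| 0.3 | 3 | 3 / 3 / 3 / 3 |
| 0.6 | 2 | 2 / 2 / 2 / 2 |
| 0.81 | 1 | 1 / 1 / 1 / 1 |
| 1.0 | 1 | 0 / 0 / 1 / 1 |
| 2.0 | 1 | 0 / 0 / 0 / 0 |
| 5.0 | 1 | 0 / 0 / 0 / 0 |

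Grades 2 to 4 are the same under both rules. Only the line between Grade 0 and Grade 1 moves.

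**Step 3: the two-grade shift.**

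| Baseline to post (GI/L) | Printed grades | Counted? | Bounded grades | Counted? |
|---|---|---|---|---|
| 2.0 to 0.9 | 1 to 1 | no | 0 to 0 (LLN 0.9) or 0 to 1 | no |
| 2.0 to 0.6 | 1 to 2 | **no** | 0 to 2 | **yes** |
| 2.0 to 0.4 | 1 to 3 | yes | 0 to 3 | yes |
| 2.0 to 0.1 | 1 to 4 | yes | 0 to 4 | yes |
| 0.85 to 0.6 | 1 to 2 | no | 1 to 2 | no |
| 0.85 to 0.4 | 1 to 3 | yes | 1 to 3 | yes |
| 0.7 to 0.1 | 2 to 4 | yes | 2 to 4 | yes |

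The bounded results for a baseline of 2.0 hold at all four assumed LLNs, apart from the labelling of 0.9 itself. Three of the six listed categories start at Grade 0 and would be empty for lymphocytes. Two of those three (0 to 3 and 0 to 4) reappear as 1 to 3 and 1 to 4. The net loss is one category, 0 to 2.

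**Step 4: would another display show it?** Normal-range shift tables (SAP Section 8.3.3) are limited to tests that have no toxicity grade. In the end-of-study addendum, 23.39 and 23.40 are the only hematology tables retained. The by-visit hematology summary is not in the list, and no safety figures are produced. A Year 2 hematology listing (23.08) remains. So does a B-cell and T-cell table (25.09), restricted to participants who completed Week 52 on treatment.

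**The case against.** The best defence is that the row summarises a named, versioned standard, cited both beside the row and in Section 8.3. Anyone grading from that source might apply a different Grade 1. The standard's text is not in the documents, so this cannot be checked. The SAP also points away from the literal reading: its shift categories presuppose a Grade 0, the row is labelled lymphopenia, and the neighbouring rows are bounded. On that view the cell is an incomplete abbreviation. The exception in Section 8.3 is explained by the missing DMID grade; it does not say that study programmers grade from this row. Finally, B cells are measured directly (SAP Section 10.1), and lymphocyte values appear in the Year 1 by-visit summaries and the hematology listings.

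Most of this stands as a limit on the consequences. It makes them conditional and keeps the importance modest. It does not clear the row. The SAP prints explicit cut-offs, those cut-offs give a wrong safety table if followed, and neither addendum corrects them. A plan should not print one rule and rely on the user to apply another.

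**Conclusion.** The printed Grade 1 cell is wrong as a grading rule: it turns every count above 0.8 GI/L into lymphopenia and leaves no Grade 0. If that row was applied, Grade 1 or higher appears in 100% of participants with a post-baseline result in every arm, and falls from normal to Grade 2 are missing from the two-grade worsening table. Falls from normal to Grade 3 or 4 are counted but mislabelled. Grade 2 to 4 classification, the Grade 3/4 listings, the data monitoring committee's Grade 3/4 review, the B-cell biomarker tables and all efficacy results are untouched.

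A reader might infer more than this:
- *That the reported tables are wrong.* The documents do not show which rule was run.
- *That study programmers must have used the row.* No section says so.
- *That the trial loses sight of B-cell depletion or severe lymphopenia.* It does not; both are captured elsewhere or correctly graded.

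The conclusion assumes that the Grade 1 cell is complete as printed. That is likely, since the other cells in the row keep their limits and LLN notation is used elsewhere in the SAP (Section 6.3). It does not depend on a particular LLN: a fall from 2.0 to 0.6 GI/L is a two-grade shift at each assumed value from 0.9 to 1.5 GI/L.

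**What to change.** In SAP Section 15.8.1, restate lymphopenia Grade 1 as below the testing laboratory's LLN and above 0.8 GI/L, and define Grade 0 as at or above the LLN. Section 8.3.3 already uses the testing laboratory's normal range to define low values, so no new reference is needed. Add a sentence in Section 8.3 saying who assigns the lymphopenia grade.

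Then check how lymphopenia was actually graded. Rerun the hematology worst-grade and two-grade worsening tables, for Year 1 and for Year 1&2, only if the code follows the printed row. If it does not, correcting the text is enough.

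The cost is one table cell, one sentence and a code check, plus a small change to the grading code and the reruns if the check calls for them. No new data are needed.

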15.9. Appendix 9: Biomarkers

| | SI BIOMARKER DATASET | | | | SDTM LB DATASET | |
|--------------------------------|----------------------|------------------------|----------|----------|-----------------|--------------------|
| Name | BICATCD | BICAT | BITESTCD | BIORRESU | LBTESTCD | LBSTRESU |
| | GSK_TestCode | GSK_TestName | | GSK_Unit | SDTM TESTCD | SDTM UNIT |
| Anti-dsDNA | ANDSAB | Anti-dsDNA antibody | CONC | IU/ML | ADSDNAAB | IU/mL |
| C3 | C3 | Complement component 3 | CONC | G/L | C3 | g/L |
| C4 | C4 | Complement component 4 | CONC | G/L | C4 | g/L |
| | | | | | | |
| | | | | | | |
| CD19+ Total B cells | CD19 | CD19+ | CONC | CELLS/ML | CD19 | 10 ³ /L |
| | | | | | | |
| B cells CD20+ | CDX111 | CD19+ CD20+ | CONC | CELLS/ML | CDX111_C | 10 ³ /L |
| B cells CD20+ | CDX111 | CD19+ CD20+ | PCTBCELL | % | CDX111_P | % |
| Naive B cells IgD+ | CDX203 | CD19+ CD27-IgD+ | CONC | CELLS/ML | CDX203 | 10 ³ /L |
| Naive B cells IgD+ | CDX203 | CD19+ CD27-IgD+ | PCTBCELL | % | CDX203 | % |
| Naive CD20+ CD27- | CDX731 | CD19+CD20+CD27- | CONC | CELLS/ML | CDX731_C | 10 ³ /L |
| Naive CD20+ CD27- | CDX731 | CD19+CD20+CD27- | PCTBCELL | % | CDX731_P | % |
| Activated Total B cells CD95+ | CDX742 | CD19+CD95b+ | CONC | CELLS/ML | CDX742_C | 10 ³ /L |
| Activated Total B cells CD95+ | CDX742 | CD19+CD95b+ | PCTBCELL | % | CDX742_P | % |
| Memory CD20+ CD27+ | CDX732 | CD19+CD20+CD27+ | CONC | CELLS/ML | CDX732_C | 10 ³ /L |
| Memory CD20+ CD27+ | CDX732 | CD19+CD20+CD27+ | PCTBCELL | % | CDX732_P | % |
| Non-switched memory CD27+ IgD+ | CDX84 | CD19+ CD27+ IgD+ | CONC | CELLS/ML | CDX84 | 10 ³ /L |

| | SI BIOMARKER DATASET | | | | SDTM LB DATASET | |
|--------------------------------------|----------------------|-------------------------------|----------|----------|-----------------|-----------|
| Name | BICATCD | BICAT | BITESTCD | BIORRESU | LBTESTCD | LBSTRESU |
| | GSK_TestCode | GSK_TestName | | GSK_Unit | SDTM TESTCD | SDTM UNIT |
| Non-switched memory CD27+ IgD+ | CDX84 | CD19+ CD27+ IgD+ | PCTBCELL | % | CDX84_PC | % |
| Switched memory CD27+ IgD- | CDX86 | CD19+ CD27+ IgD- | CONC | CELLS/ML | CDX86 | 10^3/L |
| Switched memory CD27+ IgD- | CDX86 | CD19+ CD27+ IgD- | PCTBCELL | % | CDX86_PC | % |
| Plasmablasts CD27b CD38b | CDX734 | CD19+CD27b+ CD38b+ | CONC | CELLS/ML | CDX734_C | 10^3/L |
| Plasmablasts CD27b CD38b | CDX734 | CD19+CD27b+ CD38b+ | PCTBCELL | % | CDX734_P | % |
| Plasmablasts CD20+ CD27b CD38b | CDX735 | CD19+CD20+C D27b+CD38b+ | CONC | CELLS/ML | CDX735_C | 10^3/L |
| Plasmablasts CD20+ CD27b CD38b | CDX735 | CD19+CD20+C D27b+CD38b+ | PCTBCELL | % | CDX735_P | % |
| Plasmablasts CD20- CD27b CD38b | CDX736 | CD19+CD20- CD27b+CD38b+ | CONC | CELLS/ML | CDX736_C | 10^3/L |
| Plasmablasts CD20- CD27b CD38b | CDX736 | CD19+CD20- CD27b+CD38b+ | PCTBCELL | % | CDX736_P | % |
| Transitional CD24b CD27- CD38b | CDX199 | CD19+ CD24b+ CD38b+ CD27- | CONC | CELLS/ML | CDX199 | 10^3/L |
| Transitional CD24b CD27- CD38b | CDX199 | CD19+ CD24b+ CD38b+ CD27- | PCTBCELL | % | CDX199_P | % |
| Transitional CD10+ CD24b CD27- CD38b | CDX738 | CD19+CD10+C D24b+CD27- CD38b+ | CONC | CELLS/ML | CDX738_C | 10^3/L |
| Transitional CD10+ CD24b CD27- CD38b | CDX738 | CD19+CD10+C D24b+CD27- CD38b+ | PCTBCELL | % | CDX738_P | % |
| CD3+ Total T cells | CD3 | CD3+ | CONC | GI/L | CD3 | 10^9/L |
| CD4+ T cells | CDX03 | CD3+ CD4+ | CONC | GI/L | CDX03 | 10^9/L |
| CD8+ T cells | CDX02 | CD3+ CD8+ | CONC | GI/L | CDX02 | 10^9/L |

